7.0 STUDY SCHEDULE AND ASSESSMENTS

Table 1 provides a schedule of data collection and follow-up windows. It should be noted that certain data is collected while on and/or off GERD medications.

Standard of care practices for antireflux surgery will be the basis of the assessments performed to determine if a subject is a candidate for the LINX device. Investigators should refer to the LINX Instructions for Use (IFU) for prescribing information (see **Appendix A**). Further, the study center will obtain appropriate study informed consent prior to evaluating the subject study specific evaluations. Data will then be collected at the screening/baseline visit, the implant procedure and the hospitalization period following implant until discharge. The subject will be followed at 2-weeks, 3-months, 6-months, and 12-months post-implant, with data collection occurring at each time point. Follow-up assessments may be completed by telephone or visit, with the exception of the X-rays, manometry, barium swallow, endoscopy and esophageal pH testing which must be conducted during a visit.

Subjects will complete questionnaires to evaluate reflux-related symptoms (GERD-HRQL and Foregut Symptom Questionnaire). With the exception of the GERD-HRQL

at baseline, the questionnaires are completed off GERD medications for at least 7 days, with the exception of antacids which can be taken up until the morning of assessment. At the screening/baseline visit, the questionnaires will be completed twice for the GERD-HRQL – once on GERD medications and once off GERD medications for at least 7 days, with the exception of antacids which can be taken up until the morning of assessment (Table 2).

Table 1: Schedule of Data Collection and Follow-Up Windows

Screening/ Baseline	Implant /Discharge	2-week Post-Operative Visit (Day 7 – Day 21)	3 months (Day 76 – Day 104)	6 months (Day 150 – Day 210)	12-month Visit (Day 305 – Day 425)	Data Collected
X						Demographics (gender, race)
X					X	Height and Weight
X					X	Medical History
	X					Implant Procedure and Discharge Data
X					X	Endoscopy (LA Grade Classification)
X					X	Manometry/Motility
X	X ³				X	Barium Esophagram
	X ³				X	Upright, Bi-Planar X-Rays (AP and Lateral)
X			X	X	X	GERD Medications
X ¹			X ²	X ²	X ²	GERD-HRQL
X ²			X ²	X ²	X ²	Foregut Symptom Questionnaire
X ²					X ²	Esophageal pH Measurements (off PPIs)
	X	X	X	X	X	Device and/or Procedure Adverse Events

X=All study subjects

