¹Screening/baseline GERD-HRQL questionnaire is completed twice: once on GERD medication and once off GERD medications for at least 7 days, with the exception of antacids which can be taken up until the morning of assessment.

² Completed/conducted off GERD medications for at least 7 days, with the exception of antacids which can be taken up until the morning of assessment.

³Testing performed after implant and prior to discharge or within 7 days of implant, whichever occurs first.

Table 2: Completion of Questionnaires and GERD Medication

Visit	GERD-HRQL	Foregut
Baseline/Screening	On GERD medications Off GERD medications	Off GERD medications
3-Month	Off GERD medications	Off GERD medications
6-Month	Off GERD medications	Off GERD medications
12-Month	Off GERD medications	Off GERD medications

The data detailed in **Table 3** will be obtained at each of the identified time points. Use the following guidelines provide suggested methods and documentation for testing (**Appendix B**):

- 4663 Guidelines for Endoscopy testing
- 4664 Guidelines for X-rays testing
- 4665 Guidelines for Barium Esophagram testing
- 4666 Guidelines for Manometry/Motility testing

Table 3: Planned Assessments

Visit	Assessments/Data to be Collected
Screening/ Baseline	
 • Informed Consent • Demographics (Date of Birth, Gender, Race) • Height and weight • GERD History: Duration of PPI use, Years with GERD, GERD New Onset or Pre-existing after LSG • GERD-HRQL (on/off PPIs) and Foregut Symptoms Questionnaire (off PPIs) • Baseline GERD related medication use • Esophageal pH measurements (off PPIs) • Endoscopy • Manometry/Motility • Barium Esophagram • Motivation for surgery • Inclusion/Exclusion criteria evaluation
Implant/ Discharge	
 • Surgery Date • Surgery start and stop time • Implanted device size • Concomitant procedures (e.g. hiatal hernia repair, cholecystectomy) • Barium esophagram and upright Bi-Planar X-Rays (AP and Lateral) • Discharge Date • Perioperative and device and/or procedure related adverse events
2 Week	
 • Device and/or procedure related adverse events
3-Month	
 • GERD-related medication use within the last 30 days • GERD-HRQL (off PPIs) and Foregut Symptoms Questionnaire (off PPIs) • Device and/or procedure related adverse events

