8.5.2 Quality of Life

Subjects GERD-HRQL (Health Related Quality of Life) scores will be assessed off all GERD medications. The subject's baseline GERD-HRQL score will serve as the control and be compared to the subject's GERD-HRQL 12 months post implantation.

Summary statistics will be provided for the GERD-HRQL questionnaire. Subjects are asked to rate 10 specific symptoms in addition to assessing how satisfied they are with their present condition. Each symptom is scored on a 0 to 5 scale. Summaries will also be provided for an overall score which is calculated as the average of the ten components for each subject.

Counts and percentages will be provided for responses to the GERD-HRQL questionnaire.

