8.9 Handling of Missing Data

All summaries will be performed only on enrolled subjects and only observed data will be summarized. There will be no imputation of data for early terminated subjects or for missing data within the database.

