Mean (SD)	xx.x (xx.xx)
Median(Min, Max)	xx.x (xx, xx)
95% Confidence Interval	(xx.XXX, xx.XXX)

Denominator and percentages are based on subjects completed questionnaires per protocol requirements.

Table 13
Summary of GERD-HRQL Questionnaire (Off PPI)
Full Analysis Set

Characteristic	Baseline	3 Months Follow-Up	6 Months Follow-Up	12 Months Follow-Up
Number of Subjects Completed Questionnaire per Protocol Requirements	xx	xx	xx	xx
How bad is your heartburn?				
0 - No symptoms	xx (xx.x%)	xx (xx.x%)	xx (xx.x%)	xx (xx.x%)
1 - Symptoms noticeable, but not bothersome	xx (xx.x%)	xx (xx.x%)	xx (xx.x%)	xx (xx.x%)
2 - Symptoms noticeable and bothersome, but not every day	xx (xx.x%)	xx (xx.x%)	xx (xx.x%)	xx (xx.x%)
3 - Symptoms bothersome every day	xx (xx.x%)	xx (xx.x%)	xx (xx.x%)	xx (xx.x%)
4 - symptoms affect daily activities	xx (xx.x%)	xx (xx.x%)	xx (xx.x%)	xx (xx.x%)
5 - Symptoms are incapacitating, unable to do activities	xx (xx.x%)	xx (xx.x%)	xx (xx.x%)	xx (xx.x%)
Heartburn when lying down?				
0 - No symptoms	xx (xx.x%)	xx (xx.x%)	xx (xx.x%)	xx (xx.x%)
1 - Symptoms noticeable, but not bothersome	xx (xx.x%)	xx (xx.x%)	xx (xx.x%)	xx (xx.x%)
2 - Symptoms noticeable and bothersome, but not every day	xx (xx.x%)	xx (xx.x%)	xx (xx.x%)	xx (xx.x%)
3 - Symptoms bothersome every day	xx (xx.x%)	xx (xx.x%)	xx (xx.x%)	xx (xx.x%)
4 - symptoms affect daily activities	xx (xx.x%)	xx (xx.x%)	xx (xx.x%)	xx (xx.x%)
5 - Symptoms are incapacitating, unable to do activities	xx (xx.x%)	xx (xx.x%)	xx (xx.x%)	xx (xx.x%)
Heartburn when standing up?				
0 - No symptoms	xx (xx.x%)	xx (xx.x%)	xx (xx.x%)	xx (xx.x%)
1 - Symptoms noticeable, but not bothersome	xx (xx.x%)	xx (xx.x%)	xx (xx.x%)	xx (xx.x%)
2 - Symptoms noticeable and bothersome, but not every day	xx (xx.x%)	xx (xx.x%)	xx (xx.x%)	xx (xx.x%)
3 - Symptoms bothersome every day	xx (xx.x%)	xx (xx.x%)	xx (xx.x%)	xx (xx.x%)
4 - symptoms affect daily activities	xx (xx.x%)	xx (xx.x%)	xx (xx.x%)	xx (xx.x%)
5 - Symptoms are incapacitating, unable to do activities	xx (xx.x%)	xx (xx.x%)	xx (xx.x%)	xx (xx.x%)
Heartburn after meals?				
0 - No symptoms	xx (xx.x%)	xx (xx.x%)	xx (xx.x%)	xx (xx.x%)
1 - Symptoms noticeable, but not bothersome	xx (xx.x%)	xx (xx.x%)	xx (xx.x%)	xx (xx.x%)
2 - Symptoms noticeable and bothersome, but not every day	xx (xx.x%)	xx (xx.x%)	xx (xx.x%)	xx (xx.x%)
3 - Symptoms bothersome every day	xx (xx.x%)	xx (xx.x%)	xx (xx.x%)	xx (xx.x%)
4 - symptoms affect daily activities	xx (xx.x%)	xx (xx.x%)	xx (xx.x%)	xx (xx.x%)

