Number of Subjects with at Least 50% Reduction on GERD-HRQL				xx (xx.x%)

Denominator and percentages are based on subjects completed baseline and 12 months follow-up per protocol requirements.

[1] % Successful is defined as number of subjects meeting the success criterion of at least 50% reduction on GERD-HRQL at 12 months follow-up compared to baseline off PPI.

Table 15
 Daily PPI Medication Use from Baseline to 12 Months
 Full Analysis Set

Parameter	Baseline	12 Months Follow-Up	Change from Baseline to 12 Months Follow-Up	% Successful at 12 Months Follow-Up [1]
PPI Use (mg) [2]				
n	xx	xx	xx	
Mean (SD)	xx.x (xx.x)	xx.x (xx.x)	xx.x (xx.x)	
Median (Min, Max)	xx.x (xx, xx)	xx.x (xx, xx)	xx.x (xx, xx)	
95% Confidence Interval			(xx.xxx, xx.xxx)	
Number of Subjects with at Least 50% Reduction in Daily Use				xx (xx.x%)

Denominator and percentages are based on subjects completed baseline and 12 months follow-up.

[1] % Successful is defined as number of subjects meeting the success criterion of at least 50% reduction in daily PPI use from baseline at 12 months.

[2] PPI Use is defined by the evaluation of subject's daily dose of PPI.

<Programming note those PPI administrated as PRN will not be included in daily dose calculation..>

Table 16
 Abdominal/Chest X-Ray at 12 Months Follow-Up
 Full Analysis Set

Characteristic	12 Months Follow-Up (N = ##)
Is the LINX device at the gastroesophageal junction?	
Yes	xx.x (xx.x)
No	xx.x (xx.x)
Any Evidence of Device Migration?	
Yes	xx (xx.x%)
No	xx (xx.x%)

Denominator and percentages are based on subjects with non-missing data.

Table 17
 Foregut Symptoms Questionnaire by Visit (Off PPI)
 Full Analysis Set

Characteristic	Baseline (N = ##)	3 Months Follow-Up (N = ##)	6 Months Follow-Up (N = ##)	12 Months Follow-Up (N = ##)
Regurgitation Frequency				
None	xx (xx.x%)	xx (xx.x%)	xx (xx.x%)	xx (xx.x%)
Mild	xx (xx.x%)	xx (xx.x%)	xx (xx.x%)	xx (xx.x%)
Moderate	xx (xx.x%)	xx (xx.x%)	xx (xx.x%)	xx (xx.x%)
Severe	xx (xx.x%)	xx (xx.x%)	xx (xx.x%)	xx (xx.x%)
Lung Problems				
None	xx (xx.x%)	xx (xx.x%)	xx (xx.x%)	xx (xx.x%)
Recurrent cough	xx (xx.x%)	xx (xx.x%)	xx (xx.x%)	xx (xx.x%)
Nocturnal cough	xx (xx.x%)	xx (xx.x%)	xx (xx.x%)	xx (xx.x%)
Recurrent pneumonitis	xx (xx.x%)	xx (xx.x%)	xx (xx.x%)	xx (xx.x%)
Asthma	xx (xx.x%)	xx (xx.x%)	xx (xx.x%)	xx (xx.x%)
Change of voice	xx (xx.x%)	xx (xx.x%)	xx (xx.x%)	xx (xx.x%)
Other	xx (xx.x%)	xx (xx.x%)	xx (xx.x%)	xx (xx.x%)
Ability to Vomit				

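### Table 14's GERD-HRQL responder rate omits subjects without an off-medication 12-month score, with no non-responder row beside it, so the rate may be biased upward

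*SAP*

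**What the plan says.** The Table 14 shell in the SAP appendix carries the Full Analysis Set label. It defines success as "at least 50% reduction on GERD-HRQL at 12 months follow-up compared to baseline off PPI". The footnote on the denominator reads "Denominator and percentages are based on subjects completed baseline and 12 months follow-up per protocol requirements".

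The SAP does not define those requirements. The protocol's specific condition for this questionnaire is in Section 7.0: apart from the baseline GERD-HRQL, "the questionnaires are completed off GERD medications for at least 7 days". The footnote to the schedule (Protocol Table 1) gives the same rule for the follow-up visits: "Completed/conducted off GERD medications for at least 7 days, with the exception of antacids which can be taken up until the morning of assessment". SAP 8.5.2 agrees: "Subjects GERD-HRQL (Health Related Quality of Life) scores will be assessed off all GERD medications".

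SAP Table 13 opens with a row headed "Number of Subjects Completed Questionnaire per Protocol Requirements", so it allows for questionnaires that do not qualify.

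On missing data, SAP 8.9 says "All summaries will be performed only on enrolled subjects and only observed data will be summarized" and "There will be no imputation of data for early terminated subjects or for missing data within the database". Neither 8.5.2 nor the Table 14 shell contains a non-responder rule, a sensitivity row or a count of exclusions.

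**The concern.** A subject who answers the 12-month questionnaire while taking GERD medication, or does not answer it, drops out of the rate altogether. Difficulty stopping medication for a week may be a sign that reflux is poorly controlled. To the extent that it is, exclusion depends on outcome, and the remaining subjects look better than the implanted group.

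This is one of three efficacy endpoints (Protocol 5.2). The study's aim is to show outcomes similar to those behind the premarket approval, in support of a labelling change (Protocol 3.0, SAP 1.1). With at most 30 subjects, and follow-up that SAP 8.8 describes as initially lower than anticipated, a few exclusions can move the rate visibly.

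**Working it through.** **Step 1: what the qualifier means.** The phrase is undefined, so this is an inference.

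- The GERD-HRQL tables are split by medication state: Table 12 is on PPI, Tables 13 and 14 are off PPI. The qualifier appears in all three, which fits the reading that the questionnaire was completed in the medication state the protocol prescribes for it.
- Visit windows are an unlikely meaning, because SAP Section 4 allows 12-month observations from outside the window to be analysed.
- The denominator footnotes of the other two efficacy responder tables (Table 6, pH; Table 15, PPI dose) are otherwise the same but lack the qualifier. The Foregut Symptom Questionnaire has the same washout rule, yet Tables 17 and 18 do not carry the qualifier either.
- Table 5 has a Yes/No row for 7-day discontinuation before pH testing, at baseline and at 12 months. Non-discontinuation is therefore foreseen, at least for the pH test.

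**Step 2: inputs for the size.** The plan has no figure to reproduce: SAP Section 7 states that no formal sample size calculation was done, and no expected response rate is given. Assumptions: 24 subjects reach 12 months; about 80% of washed-out subjects respond; 2, 4 or 6 subjects are not washed out.

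Let m = washed-out completers, r = responders among them, k = excluded subjects, and x = excluded subjects who would have responded off medication.

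- Table 14 rate: r/m
- Rate over all m + k subjects: (r + x)/(m + k)
- Inflation: r/m − (r + x)/(m + k). It is largest at x = 0 and zero when x/k = r/m.

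| k | Table 14 rate | None respond (x = 0) | Inflation | Half respond (x = k/2) | Inflation |
|---|---|---|---|---|---|
| 2 | 18/22 = 81.8% | 18/24 = 75.0% | 6.8 | 19/24 = 79.2% | 2.7 |
| 4 | 16/20 = 80.0% | 16/24 = 66.7% | 13.3 | 18/24 = 75.0% | 5.0 |
| 6 | 14/18 = 77.8% | 14/24 = 58.3% | 19.4 | 17/24 = 70.8% | 6.9 |

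Inflation is in percentage points. The sign can reverse: with k = 4 and all four responding, the full rate is 20/24 = 83.3%, and Table 14 understates it by 3.3 points.

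**Step 3: the same comparison over 30 implanted subjects.** Suppose 5 have no valid off-medication 12-month score for any reason, and 20 of the other 25 respond (assumed). The completer rate is 20/25 = 80.0% (exact 95% CI 59.3 to 93.2). Counting the five as not successful gives 20/30 = 66.7% (47.2 to 82.7).

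**Step 4: would scoring on-medication questionnaires solve it?** No. Inclusion criterion 7 admits subjects because they score better on PPI. Measured against an off-PPI baseline, an on-PPI score can meet the 50% criterion through the drug alone: 20 to 10 is a 50.0% fall and 30 to 10 is 66.7%, although 15 to 10 is only 33.3%.

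**The case against.** The strongest reply is that the restriction protects the measurement. The endpoint is defined off PPI, and Step 4 shows that admitting on-medication scores could create false responders. That stands. What remains open is only how to count a subject with no valid off-medication score.

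A reader might infer that the table removes subjects who cannot stop their PPI and counts only those who can live without one. The documents do not support that. At entry, with untreated reflux, every eligible subject had to complete pH testing after at least 7 days off GERD medication and have symptoms off PPI (inclusion criteria 6 and 8), and the schedule requires an off-medication GERD-HRQL. Antacids are allowed until the morning of assessment. At 12 months a daily PPI user who pauses for a week stays in the table. Forgetting, refusing, or answering by telephone without having stopped (Section 7.0 allows telephone completion of questionnaires) are all plausible reasons for non-washout that need not reflect device failure.

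It is also true that PPI use is visible elsewhere. Table 15 is its own efficacy endpoint, Tables 3 and 29 show use by visit, Table 13 prints the number completing as required, Table 14 prints n, and the listings give subject-level data. A high GERD-HRQL rate could not hide continuing PPI use. But none of these tables corrects the Table 14 rate or says why subjects are absent from it.

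Finally, observed-data analysis is prespecified in a descriptive study (Protocol 10.0 and 10.4, SAP 8.9). That makes the completer rate a legitimate row. It does not make it sufficient on its own under a Full Analysis Set label.

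**Conclusion.** The point holds as a conditional one. On the most plausible reading, Table 14 is narrower than its label, and subjects not washed out at 12 months disappear from the rate without any replacement rule. The rate is expected to be biased upward if those subjects respond less often off medication than completers. That is plausible, but the documents do not establish it.

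A reader might go further and say that the rate is inflated by 7 to 19 points. The documents do not support that: these figures are the ceiling, reached only if no excluded subject would have responded. Under the assumptions above (24 at 12 months, about 80% response, 2 to 6 exclusions), the bias is about 3 to 7 points if half would have responded, zero if they respond as completers do, and slightly negative if all would have. The documents give neither the number of such subjects nor a response rate, so the actual size is unknown. This is a cheap improvement to one of three efficacy endpoints, not a flaw that invalidates it.

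**What to change.** In Table 14:

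1. State in the footnote that completion as the protocol requires means at least 7 days off GERD medication, antacids excepted. Continue not to score on-medication questionnaires as responses.
2. Keep the present off-medication completer rate as one row.
3. Add a row whose denominator is all FAS subjects with an off-PPI baseline score. Count as not successful anyone without a valid off-medication 12-month score, including explanted subjects, for whom Protocol 11.9 requires no further questionnaires.
4. Give exact 95% confidence intervals for both rows, by the Clopper-Pearson method that SAP 8.5.1 already names for the pH endpoint.
5. Report the number excluded from the completer row by reason (on medication, explanted, lost to follow-up or missing) and how many were taking a PPI, where known.

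The cost is SAP wording and a few table rows. Medication status at the questionnaire is already needed to fill the Table 13 count, and 12-month PPI use is already in Table 3. The case report forms are not among the documents, so the sponsor should confirm that the reason for a missing off-medication score can be derived.

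The downside is a less favourable second rate, in which a subject who merely forgot the washout or was lost to follow-up counts as a failure. The second row is a floor. The two rows bracket the full rate provided that excluded subjects respond no more often than completers.

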5.2 ASSESSMENT OF EFFICACY

Efficacy will be assessed by evaluating the percentage of subjects reporting at the 12-month follow-up:

- Normalization of total distal acid exposure time or at least 50% reduction in total distal acid exposure time compared to baseline
- $\geq 50\%$ reduction in total GERD-HRQL score compared to baseline (off PPIs)
- $\geq 50\%$ reduction in average daily PPI dosage compared to baseline

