10.1.3 USE OF PPIS

Subject's average daily dose of PPI will be evaluated. The subject's baseline average daily dosage will serve as the control and be compared to the subject's average daily dosage 12 months post-procedure.

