8.5.3 Use of PPIs

Subject's average daily dose of PPI will be evaluated. The subject's baseline average daily dosage will serve as the control and be compared to the subject's average daily dosage 12 months post-procedure.

The proportion of subjects with at least 50% reduction in daily PPI use from baseline at 12 months will be reported. In addition, a two-sided 95% CI will be provided for the proportion of success (>=50% reduction achieved).

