Omeprazole	xx (xx.x%)	xx (xx.x%)	xx (xx.x%)	xx (xx.x%)
Aspirin/Omeprazole	xx (xx.x%)	xx (xx.x%)	xx (xx.x%)	xx (xx.x%)
Omeprazole/Sodium bicarbonate	xx (xx.x%)	xx (xx.x%)	xx (xx.x%)	xx (xx.x%)
Lansoprazole	xx (xx.x%)	xx (xx.x%)	xx (xx.x%)	xx (xx.x%)
Dexlansoprazole	xx (xx.x%)	xx (xx.x%)	xx (xx.x%)	xx (xx.x%)
Rabeprazole	xx (xx.x%)	xx (xx.x%)	xx (xx.x%)	xx (xx.x%)
Pantoprazole	xx (xx.x%)	xx (xx.x%)	xx (xx.x%)	xx (xx.x%)
Esomeprazole	xx (xx.x%)	xx (xx.x%)	xx (xx.x%)	xx (xx.x%)
Other	xx (xx.x%)	xx (xx.x%)	xx (xx.x%)	xx (xx.x%)
Currently Taking H2 Blocker				
Yes	xx (xx.x%)	xx (xx.x%)	xx (xx.x%)	xx (xx.x%)
No	xx (xx.x%)	xx (xx.x%)	xx (xx.x%)	xx (xx.x%)
H2 Blocker Medication				
Nizatidine	xx (xx.x%)	xx (xx.x%)	xx (xx.x%)	xx (xx.x%)
Famotidine	xx (xx.x%)	xx (xx.x%)	xx (xx.x%)	xx (xx.x%)
Cimetidine	xx (xx.x%)	xx (xx.x%)	xx (xx.x%)	xx (xx.x%)
Ranitidine	xx (xx.x%)	xx (xx.x%)	xx (xx.x%)	xx (xx.x%)
Other	xx (xx.x%)	xx (xx.x%)	xx (xx.x%)	xx (xx.x%)
Currently Taking Antacids				
Yes	xx (xx.x%)	xx (xx.x%)	xx (xx.x%)	xx (xx.x%)
No	xx (xx.x%)	xx (xx.x%)	xx (xx.x%)	xx (xx.x%)

Denominator and percentages are based on subjects with non-missing data.

<Programming note: Only categories observed in the database need to be displayed for PPI and H2 medications>

Table 4
LSG and GERD History
Full Analysis Set

Characteristic	Total (N = ##)
GERD new-onset after LSG or pre-existing	
Pre-existing	xx (xx.x%)
New-onset	xx (xx.x%)
Duration of having GERD (years)	
n	xx
Mean (SD)	xx.x (xx.x)
Median (Min, Max)	xx.x (xx, xx)
Duration of taking PPIs (years)	
n	xx
Mean (SD)	xx.x (xx.x)
Median (Min, Max)	xx.x (xx, xx)
BMI on date of LSG (kg/m ²)	
n	xx
Mean (SD)	xx.x (xx.x)
Median (Min, Max)	xx.x (xx, xx)
Time between LSG surgery and LINX implant (days)	
n	xx
Mean (SD)	xx.x (xx.x)
Median (Min, Max)	xx.x (xx, xx)

Denominator and percentages are based on subjects with non-missing data.

Table 5
 Characteristics of pH Results (Off PPI)
 Full Analysis Set

Characteristic	Baseline (N = ##)	12 Months Follow-Up (N = ##)
Was GERD Medications discontinued at least 7 days prior to test?		
Yes	xx (xx.x%)	xx (xx.x%)
No	xx (xx.x%)	xx (xx.x%)
Type of pH Testing Method Used		
Bravo capsule	xx (xx.x%)	xx (xx.x%)
5 cm above manometry upper border of the LES	xx (xx.x%)	xx (xx.x%)
6 cm above endoscopically visualized SCJ	xx (xx.x%)	xx (xx.x%)
Trans-nasal catheter	xx (xx.x%)	xx (xx.x%)
Trans-nasal with impedance catheter	xx (xx.x%)	xx (xx.x%)
pH Test Duration (days)		
n	xx	xx
Mean (SD)	xx.x (xx.x)	xx.x (xx.x)

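### SAP Table 15 pools PPI dose in raw milligrams across different products with no conversion or switching rule, so the mean depends on product mix and subjects who change product can be misclassified on the 50% rule

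*SAP*

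**What the plan says.** Protocol section 5.2 makes a 50% "reduction in average daily PPI dosage compared to baseline" one of three efficacy endpoints at 12 months. Protocol section 10.1.3 adds that "Subject's average daily dose of PPI will be evaluated", with the baseline value as control. It names no unit.

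SAP section 8.5.3 repeats this and adds: "The proportion of subjects with at least 50% reduction in daily PPI use from baseline at 12 months will be reported". It also says that "a two-sided 95% CI will be provided for the proportion of success". Again no unit is named.

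The unit appears only in the SAP appendix. Table 15 has a single PPI row in milligrams, with n, mean, SD, median, range, change from baseline, a 95% confidence interval for the change, and the responder count. Its footnote reads "PPI Use is defined by the evaluation of subject's daily dose of PPI". The only calculation rule is a programming note that "those PPI administrated as PRN will not be included in daily dose calculation".

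SAP Table 3 tabulates PPI products at baseline, 3, 6 and 12 months. It names eight products plus an other category. Three of the eight contain omeprazole, so there are six PPI substances. Two are combinations, for example "Omeprazole/Sodium bicarbonate". Table 3 also has a row headed "Currently Taking H2 Blocker".

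**The concern.** Adding or comparing milligrams across products treats one milligram of each as equal to one milligram of any other. The SAP neither states nor justifies that. Protocol section 9.2 gives reduced dependence on GERD medication as an intended benefit. A change of product can alter the milligrams without altering that dependence, or alter the dependence without altering the milligrams.

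Two outputs are exposed to different degrees. The pooled mean and mean change mix products across all subjects, so they are affected even if nobody switches. The responder rule is a within-subject percentage, so the unit cancels unless the subject changed product. A further gap is that Table 15 does not say whose milligrams count for a two-component product.

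**Working it through.** The documents contain no expected PPI response, sample size calculation or relative strengths, so there is no planned figure to reproduce. The check is how the stated rule behaves.

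**Inputs**
- 50% threshold: Protocol 5.2 and SAP 8.5.3.
- Milligram unit: SAP Table 15.
- Up to 30 subjects: Protocol section 5.0 and SAP section 7. The denominator is subjects with both baseline and 12-month data (Table 15). SAP 8.8 reports lower than anticipated follow-up and SAP 8.9 imputes nothing, so a smaller n is plausible; n=20 is an assumption.
- r, the strength per milligram of the 12-month product relative to the baseline product: not in the documents, assumed 0.5 to 2.

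**Responder rule.** Let q = 12-month mg ÷ baseline mg. Raw reduction = 1 − q. Effective reduction = 1 − r·q.

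| r | q | Raw reduction | Effective reduction | Scored as | On effective dose |
|---|---|---|---|---|---|
| 2 | 0.5 | 50% | 0% | success | failure |
| 1.5 | 0.5 | 50% | 25% | success | failure |
| 1 | 0.5 | 50% | 50% | success | success |
| 0.5 | 0.5 | 50% | 75% | success | success |
| 0.5 | 0.75 | 25% | 62.5% | failure | success |
| 0.5 | 1 | 0% | 50% | failure | success |
| any | 0 | 100% | 100% | success | success |

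A false success needs q ≤ 0.5 and r·q > 0.5, hence r > 1. A false failure needs q > 0.5 and r·q ≤ 0.5, hence r < 1. With r = 1 (same product) or q = 0 (no scheduled PPI), the two classifications always agree.

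**Effect on the rate.** One misclassified subject moves it by 1/30 = 3.3 points, or 1/20 = 5 points. As an illustration, assume 24/30 = 80.0% responders, with exact 95% interval 61.4% to 92.3% (SAP 8.5.3 names no interval method for this endpoint). Removing two false successes gives 22/30 = 73.3% (54.1% to 87.7%).

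**Pooled mean, with switching.** Suppose all 30 start on one product at one dose and 6 change to an equal-effect dose of another, which is 1/r of the old milligrams. The mean changes by (6/30) × (1/r − 1):
- r = 2: −10.0%
- r = 1.5: −6.7%
- r = 0.5: +20.0%

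Acid suppression is unchanged in each case. The six switchers are an assumption.

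**Pooled mean, without switching.** Let product B be twice as strong per milligram as A, with equal-effect doses D of A and D/2 of B. If every subject stops PPI, the mean change is −D when all were on A, −D/2 when all were on B, and −0.75·D for an even split. The effective change is the same in all three.

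**The case against.** The strongest reply is that the problem may be very small. The endpoint proper is the responder proportion; the mean is supporting description, shown beside the median. Only subjects still on a scheduled daily PPI at 12 months and on a different product can be misclassified, and then only if the raw and converted ratios fall on opposite sides of 50%. Table 3 is a menu: its programming note requires display only of categories that occur. SAP Table 29 reports discontinuation of daily PPI at each follow-up, which needs no milligrams. The study has no formal hypothesis and no success threshold for this rate, and the pH and GERD-HRQL endpoints are assessed off PPIs. The use of raw milligrams is itself inferred from the unit and the absence of any conversion rule.

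All of this stands as a limit on size. It does not supply the missing rule. If conversion was intended, the SAP does not say so, and two programmers could reach different results. The dependence of the mean on product mix remains even with no switchers.

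Three stronger readings are tempting but not supported:
- A reader might infer that the percentage change is meaningful only for subjects on the same drug at both visits. It is also exact for anyone who stopped.
- A reader might infer that H2 blocker use cannot be linked to PPI responders because Table 3 shows it only in aggregate. SAP section 8.1 lists all eCRF data per subject, and Listings 10 and 17 cover GERD medications at baseline and follow-up. Only a planned summary is missing.
- A reader might infer that a subject who moves from a PPI to an H2 blocker should be a non-responder. Both documents define the endpoint as PPI dosage, so that would widen it. Table 3 also records H2 use as yes or no by agent, without dose or frequency, so occasional use would count as failure.

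**Conclusion.** The point holds in limited form. As written, the pooled mean and mean change in milligrams are not interpretable as a measure of acid-suppression burden, because they vary with product mix. The responder classification can be wrong in either direction, but only for subjects on a different scheduled daily PPI at 12 months. The documents do not support a general claim that the responder rate is unreliable.

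The cost is 3.3 points per misclassified subject at n=30, or 5 points at the assumed n=20. The net size and direction are unknown, since they depend on the number of switchers, which may be zero, and on relative strengths that the documents do not give. The plan should be changed before analysis, but the gap does not undermine the study's other endpoints.

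**What to change.** Before analysis, specify in the SAP:
- One common unit for daily PPI dose, with a cited conversion table chosen by the sponsor. Multiples of each product's labelled standard daily dose would be one example.
- For combination products, only the PPI component counts.
- That unit is used for the Table 15 summary and for the 50% rule.
- The number of subjects who changed product between baseline and 12 months is reported, with a sensitivity result limited to subjects on the same product or free of PPI.
- At most, a descriptive count of PPI responders who report H2 blocker use at 12 months, without reclassifying them.

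The cost is a short conversion table and a few output rows. Tables 3 and 15 already require product and dose by visit. The change alters how an endpoint is calculated, so it does not fit the allowance in SAP section 8.1 for minor table modifications without an amendment. The downside is that any conversion is approximate; the same-product or PPI-free result shows how much depends on it.
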